### 3.5.3 Evaluable Population – Immunogenicity Analysis

The Evaluable Population for immunogenicity analyses will comprise all subjects in the FAS who:

- receive vaccine at Visit 1;
- provided serology specimens which provided valid serology assay results from both Visit 1 and the Study Exit Visit (Visit 2 or 3);

- did not experience a laboratory-confirmed influenza illness between Visit 1 and Study Exit Visit (Visit 2 or 3); and
- did not receive any prohibited medication during the study that is medically assessed to potentially impact immunogenicity results.

### 3.5.4 Per-Protocol Population

The Per-Protocol Population (PPP) will comprise all subjects in the Evaluable Population who do not have any protocol deviations that were medically assessed as potentially impacting on immunogenicity results.

The Per Protocol Population will be the primary population of interest for the primary immunogenicity analysis and a supporting analysis will be performed using the Evaluable Population.

Membership of the PPP will be determined prior to unblinding the study.

Primary and secondary immunogenicity analyses will be completed using the Per-Protocol Population. Duplicate tables of primary and secondary immunogenicity analyses may also be produced based on the Evaluable population if there is >1% difference in the total number of subjects in either of the two age-strata (6 through 35, and 36 through 59 months) between the Per-Protocol Population and the Evaluable Population. The decision to produce tables based on the Evaluable Population will be made by Seqirus after population sets are finalised and prior to unblinding. Analysis on antipyretics frequency will be performed on the Per-Protocol Population.

The study biostatistician will provide information on proposed datasets to Seqirus for review. Protocol deviation listings will also be reviewed by Seqirus prior to the finalisation of the population datasets, which will occur prior to unblinding. The lists will be used to determine which subjects should be excluded from either the Evaluable or the Per Protocol Population, with documentation of the reason for exclusion.

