 - *Seroconversion.* For each strain the subjects will be classified as 'seroconverted' if either they have a prevaccination HI antibody titer < 1:10 and a postvaccination HI antibody titer \geq
-

1:40 or a prevaccination HI antibody titer \geq 1:10 and a \geq 4-fold increase in postvaccination HI antibody titer. Otherwise they will be classified as ‘not seroconverted’;

- *Seroprotection*. For each strain a subject will be classified as ‘seroprotected’ if their HI antibody titer \geq 1:40 at Days 1 and the Study Exit Visit. If they do not have both antibody titers \geq 1:40 they will be classified as ‘not seroprotected’;
- *Fold increase*. For each strain the fold increase for each subject will be calculated by taking the ratio of the postvaccination antibody titer over the prevaccination antibody titer;

Covariate adjusted analyses will be performed as outlined in the Statistical Analysis Plan (SAP).

Immunogenicity Analyses (Day 1 and Study Exit Visit):

Immunogenicity analyses in terms of HI antibody titers specific for the virus strains included in the vaccines will be performed on serum specimens taken at Day 1 (Visit 1) and at the Study Exit Visit (Visit 2 – single dose schedule or Visit 3 – two-dose schedule).

Safety Assessments

Safety will be assessed through solicited local reactions, solicited systemic AEs, unsolicited AEs, and SAEs.

Type, frequency and intensity of solicited local reactions through Day 7 (Day 1, 2, 3, 4, 5, 6, 7) following each study vaccination dose. These include pain, erythema/redness, and induration/swelling.

Frequency of cellulitis-like reaction for 28 days following each vaccination. Cellulitis-like reaction is defined as the concurrent presence of grade 3 injection site pain, erythema/redness and induration/swelling.

Type, frequency, duration and intensity of solicited systemic AEs through to Day 7 (Day 1, 2, 3, 4, 5, 6, 7) following each study vaccination dose. These include headache, malaise and fatigue, myalgia, fever, diarrhea, and nausea and/or vomiting for children 36 months through 59 months of age, and fever, diarrhea, nausea and/or vomiting, loss of appetite, and irritability for children 6 months through 35 months of age.

Frequency of antipyretic use in the 7 days after each vaccination dose

Type, frequency, duration and intensity of unsolicited AEs for at least 28 days following each study vaccination dose.

	Frequency of SAEs and AESIs for at least 180 days following the last vaccination dose.

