11.2.2 Safety Population

The Safety Population will comprise all subjects in the FAS who received at least one dose or partial dose of Study Vaccine and have provided any evaluable follow-up safety data. The safety population will be used to produce summaries and listings of all safety data.

Follow-up safety data is defined as any safety information that is recorded for a subject in a Study Diary or in the subject's medical notes.

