## 2.3 Exploratory Objectives and Endpoints

### 2.3.1 Exploratory Objectives

The exploratory objective of the study is:

- To assess the frequency of antipyretic use in the first 7 days post vaccination in two age strata: 6 months through to 35 months, and 36 months through 59 months, as well as overall according to treatment group.

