### 3.5.2.2.1 Solicited Safety Population after the First Vaccination

The Solicited Safety Population after the First Vaccination will comprise all subjects in the FAS who received at least one dose or partial dose of the first vaccination of Study Vaccine and have provided any evaluable data on solicited events after the first vaccination. This safety population will be used in the assessment of solicited AEs after the first vaccination.

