### 3.5.2.2.2 Solicited Safety Population after the Second Vaccination

The Solicited Safety Population after the Second Vaccination will comprise all subjects in the FAS who received at least one dose or partial dose of the second vaccination of Study Vaccine and have provided any evaluable data on solicited events after the second vaccination. This safety population will be used in the assessment of solicited AEs after the second vaccination.

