### 4.13 Changes in Conduct or Planned Analyses from the Protocol

The term 'sex' has been replaced with 'gender' throughout the analysis section. The safety population has been refined for overall, solicited safety, solicited safety after 1st vaccination and solicited safety after 2nd vaccination.

The term Number of Doses (1 vs 2) has been included as an additional covariate in the GLM model fitting.

There will be no separate summary tables for SAEs by maximum intensity and relationship, discontinuations due to AEs related to Study Vaccine, or discontinuations due to SAEs. These details will be in listings only.

Unsolicited AEs will be presented overall and not after each vaccination dose, as stated in the secondary endpoints. The wording in the endpoint should have been 'Frequency and severity of unsolicited AEs for at least 28 days (ie, day of vaccination and 27 subsequent days) after the last vaccination dose'.

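### Minor: Day 1–7 antipyretic use is tabulated in the Per-Protocol Population, so its denominators differ from those of the solicited fever tables, and SAP 4.13 does not record the choice

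*SAP*

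**What the plan says.** The exploratory objective (SAP 2.3.1) begins "To assess the frequency of antipyretic use in the first 7 days post vaccination in two age strata" and continues with the overall population and treatment group. It makes no mention of serology.

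On the population, the two documents point in different directions:

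- SAP 3.5.4: "Analysis on antipyretics frequency will be performed on the Per-Protocol Population".
- SAP 3.5.3 and 3.5.4: the Per-Protocol Population is a subset of the Evaluable Population, whose members "provided serology specimens which provided valid serology assay results from both Visit 1 and the Study Exit Visit (Visit 2 or 3"). They must also have had no laboratory-confirmed influenza and no prohibited medication or deviation medically judged able to affect immunogenicity.
- Protocol synopsis and 10.3, both under Safety Assessments: "Frequency of antipyretic use in the 7 days after each vaccination dose".
- Protocol 11.2.2: "The safety population will be used to produce summaries and listings of all safety data".
- SAP 3.5.2.2.1, on solicited events (which include fever): "This safety population will be used in the assessment of solicited AEs after the first vaccination". SAP 3.5.2.2.2 says the same for dose 2: "This safety population will be used in the assessment of solicited AEs after the second vaccination". These sets require a dose and some solicited data, not serology.
- SAP 4.13, on changes from the protocol: "The safety population has been refined for overall, solicited safety, solicited safety after 1st vaccination and solicited safety after 2nd vaccination". It says nothing about antipyretics.

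SAP 4.7.5 describes the antipyretic tables but names no population. SAP 4.1 assigns sets to the safety, primary and secondary analyses and none to exploratory ones.

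**The concern.** Antipyretic use in the first week is naturally read beside fever in the first week. Protocol 1.1.2 and 1.4 describe febrile reactions in children under 5 after the company's earlier trivalent vaccine, so this comparison is an obvious one for a reader to make. As planned, the two sets of tables cover different children.

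The main route is missing paired serology. A child may be vaccinated, supply Day 1–7 data and then leave before the Exit Visit; SAP 3.6 gives an adverse event as one possible reason. That child is in the fever tables and absent from the antipyretic tables.

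A second route is only possible. Prophylactic antipyretics on the day of vaccination or in the following week are prohibited (SAP 3.4). A child who received one could be removed because of the very use being counted. This needs a medical judgement that immunogenicity may be affected; a major deviation does not by itself remove a child (SAP 4.10), and use to treat adverse events is allowed.

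At stake is the interpretability of two descriptive tables. No test or margin depends on them.

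**Working it through.** **Who is counted where**

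| Requirement | Fever after a dose (SAP 3.5.2.2) | Antipyretic use (SAP 3.5.3, 3.5.4) |
|---|---|---|
| Vaccinated | at that dose | at Visit 1 |
| Any solicited data | yes | not required |
| Valid serology at Visit 1 and Exit Visit | not required | yes |
| No laboratory-confirmed influenza | not required | yes |
| No medication or deviation judged to affect immunogenicity | not required | yes |

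The Per-Protocol definition requires vaccination only at Visit 1. The SAP does not say whether the second-dose antipyretic rows are limited to children who received a second dose. Nor does it say whether the Per-Protocol Population is analysed as randomised (stated for the Full Analysis Set, SAP 3.5.1) or as treated (stated for the Overall Safety Population, SAP 3.5.2.1).

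**Possible size**

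The only relevant planning figures are in Protocol 11.1 and SAP 3.9: 2000 evaluable, 2222 enrolled, 10% dropout.

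- Check of the plan's figure: 2000 / 0.90 = 2222.2, which agrees with 2222.
- Planned gap: 2222 − 2000 = 222, and 222 / 2222 = 9.99%, taken as 10%.

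This 10% is a planning allowance and not a ceiling. Among children with Day 1–7 data the share outside the Per-Protocol Population may be smaller, since some dropouts will have no such data. Exclusions for reasons other than dropout could push it the other way.

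Let e be the share outside, p the use inside and g the use among those outside. Then

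Per-Protocol rate − all-children rate = p − [(1 − e)p + e·g] = e(p − g).

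The documents give neither p nor g. Assuming p = 20%:

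| e | g = 10% | g = 20% | g = 30% |
|---|---|---|---|
| 10% | +1.0 point | 0 | −1.0 point |
| 5% | +0.5 point | 0 | −0.5 point |

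Between arms, the change in (Seqirus − Comparator) is e_S(p − g_S) − e_C(p − g_C). With p = 20% and the same e in both arms:

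| g_S, g_C | e = 10% | e = 5% |
|---|---|---|
| equal | 0 | 0 |
| 30%, 20% | −1.0 point | −0.5 point |
| 20%, 30% | +1.0 point | +0.5 point |

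For the conditional prophylactic route, suppose a share f of all children are users and are removed for that use, with a true rate of 20%. The Per-Protocol rate is (0.20 − f)/(1 − f):

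- f = 1%: 0.19/0.99 = 19.2%
- f = 2%: 0.18/0.98 = 18.4%
- f = 5%: 0.15/0.95 = 15.8%

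These values of f are chosen only to show scale.

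**The case against.** The strongest reply is that nothing is breached. Protocol 10.3 opens by saying safety is assessed through solicited reactions and events, unsolicited events and serious events; antipyretic use is not among them. It is a separate exploratory endpoint with no population named, and Protocol 11.2 and 11.3.2.2 leave further detail to the SAP. SAP 5.3.2 lists the two tables under Immunogenicity, consistent with 3.5.4. On that reading the SAP filled a gap, and 4.13 had nothing to record. Because antipyretics are reviewed for effects on immunogenicity, describing their use in the immunogenicity set is defensible. Membership is also fixed before unblinding.

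Much of this stands. It is why the point is an unexplained inconsistency and not a clear departure from protocol. Three parts do not settle it. Listing under Immunogenicity does not determine the set: Influenza-Like Illness (Table 14.2.6) is in the same list and uses the Full Analysis Set (SAP 4.7.3.1). The SAP gives no immunogenicity reason, and SAP 4.7.5 plans only counts, percentages, exact limits and days of use, with no link to titers. Fixing membership early prevents data-driven selection but does not align denominators.

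Two mitigations are fair. Protocol 4.2.2 calls for attempts to complete the final assessment, and 7.1 asks children contraindicated for dose 2 to complete an Exit Visit; these narrow the withdrawal route without closing it. Use outside the Per-Protocol Population will also appear in Listing 16.2.4.4 and possibly in the concomitant medication tables (SAP 4.6), but neither replaces a Day 1–7 endpoint table.

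It is also true that the Solicited Safety Populations are defined by solicited fields and not by the Medication Diary. The fix has to allow for that.

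**Conclusion.** The point holds and is minor. The plan measures first-week antipyretic use in a set that requires serology about four weeks after the last dose, while the matching fever tables do not, and no reason is given. The size and direction of any effect cannot be derived from the documents. Under the assumed 20% use, with 5% to 10% of children outside the set and use among them within 10 points of that, the rate or the arm difference would shift by 0 to 1.0 point. Exclusion of prophylactic users could move it further, but only if the medical review removes them. If exclusion is unrelated to use, the shift is nil. The primary noninferiority conclusion is not affected.

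**What to change.** In SAP 3.5.4 and 4.7.5, for Tables 14.2.7.1 and 14.2.7.2:

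- Dose-specific rows: use children vaccinated at that dose who are in the Solicited Safety Population for that dose.
- Row covering either dose: use the Solicited Safety Population.
- State that analysis is by vaccine received. SAP 3.5.2.2 does not say this for the solicited sets, so it needs to be written out.
- For each row, give the number of children with no Medication Diary record, because SAP 3.5.2.3 defines these sets by local symptom, temperature and systemic symptom fields.
- Keep a Per-Protocol version only as supportive, and enter the choice and its reason in SAP 4.13.

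Separating prophylactic from treatment use is optional. The cost is two or three sentences, new population flags for two tables and one added count, with no new data. The small downside is that some children in the denominator may have no medication record; the added count makes that visible.

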## 3.6 Withdrawn Subjects

Subjects may withdraw from the study at any time at their own request or request of the parent or legally appropriate representative, or they may be withdrawn at any time at the discretion of the investigator or Seqirus for safety, behavioural or administrative reasons (eg, due to an adverse event, protocol deviation, loss to follow-up, subject noncompliance to protocol procedures, and study termination).

In accordance with ICH principles of Good Clinical Practice (GCP) the investigator always has the option to advise a subject to withdraw from the study if the subject's safety or wellbeing is compromised by his or her further participation in the study. Concern for the interests of the subject must always prevail over the interests of the study.

If a subject is withdrawn from the study or further participation is declined, they will continue to have access to medical care and will be treated as per routine medical practice.

## 3.7 Randomisation

A randomization scheme will be used to ensure that the balance between the treatment groups is maintained. To ensure the study blind is maintained, delegates from the Interactive

Response Technology (IRT) company, in association with a Seqirus statistician/delegate not directly involved in the analysis of study results, will prepare the study randomization code. The Stability and Environmental Monitoring group at Seqirus will keep a checked final copy of the randomization code on file. Emergency Code Break IRT access will be provided to the investigational site for use in case of an emergency.

Eligible subjects will be randomized by means of IRT to one of the 2 treatment groups in a 3:1 ratio (Seqirus QIV: Comparator QIV) and will be proportionally balanced in the two age strata (6 through 35 months and 36 through 59 months), with no more than 60% of the total sample size represented in one age stratum. The IRT system will manage randomization and provide to the sites a subject randomization number. The number will correspond to the appropriate study treatment.

### 3.8 Blinding

Investigational site staff including the investigator and all personnel performing study assessments will be blinded to treatment allocation (observer-blind). The subject and parent(s)/ guardian(s) will also remain blinded to treatment allocation.

As there is a visual difference between the Seqirus QIV and the Comparator QIV pre-filled syringes, personnel who prepare and administer the Study Vaccine will be considered unblinded and excluded from involvement in other study procedures, with the exception of other Study Vaccine related activities, such as receipt, preparation and accountability management.

All Seqirus study staff, excluding those in the Seqirus Stability and Environmental Monitoring group and Quality Assurance group, will also be blinded to treatment allocation. Study monitors will be blinded to subject treatment allocation and will remain blinded when performing Study Vaccine accountability.

The randomization code will be unblinded four times:

1. at the time of the safety analysis after a third of subjects or a minimum of 300 subjects in the 36 months through 59 months of age cohort have been enrolled;
2. at the time of the safety analysis after a third of subjects or a minimum of 300 subjects in the 6 months through 35 months of age cohort have been enrolled
3. at the time of the interim analysis when all subjects have completed all immunogenicity assessments and all solicited and unsolicited adverse event reporting;
4. and finally, once all data (including extended follow-up for recording SAEs and AESIs) have been entered into the study database for each subject and the database has been locked.

The randomization code will be provided to the Biostatistics group once written authorization of database lock has been received.

The first unblinding will occur after a third of subjects or a minimum of 300 subjects in the 36 months through 59 months of age cohort are enrolled. A Data and Safety Monitoring Board (DSMB) will review and assess available unblinded safety data in a closed session. The Seqirus team will remain blinded.

The second unblinding will occur after a third of subjects or a minimum of 300 subjects in the 6 months through 35 months of age cohort are enrolled. The DSMB will review and

assess available unblinded safety data in a closed session. The Seqirus team will remain blinded.

Unblinding of the randomization code will also occur once all subjects have completed all immunogenicity assessments and all solicited and unsolicited adverse event reporting. This will facilitate timely analysis of immunogenicity and safety data including all solicited AEs. The results may be communicated to regulatory authorities and relevant personnel within Seqirus but not to personnel directly involved in monitoring the study or interacting with investigators. The results will not be communicated to investigators. Seqirus Safety personnel participating in review of the interim analysis will have no further involvement in the assessment of any SAEs occurring after interim database lock.

A final clinical study report will present all immunogenicity and safety data collected from the active study period and safety data through to the final evaluation (180 days following the last vaccination dose).

Seqirus Safety personnel may unblind the randomization code for an individual subject at any time to facilitate assessment of suspected unexpected serious adverse reactions (SUSARs) experienced by any subject for expedited reporting to regulatory authorities. To maintain integrity of the study blind the Seqirus Safety personnel responsible for assessment of SUSARs are excluded from the Seqirus study team.

### 3.9 Sample Size

Seqirus QIV will be tested against a US-licensed comparator QIV. The treatment randomization ratio is 3:1 (Seqirus QIV: Comparator QIV).

This study is designed to achieve at least 80% power to demonstrate noninferiority for all of the 8 co-primary endpoints, seroconversion rates for 4 strains, GMT for 4 strains using a one-sided alpha of 0.025 for each comparison. No adjustment for multiple endpoints was made. For comparisons of SCR a noninferiority margin of 10% (Comparator QIV-Seqirus QIV) will be employed. It is assumed that the SCR for all strains for QIV is 50% and that there is no difference between Seqirus QIV and Comparator QIV.

For comparison of GMT ratio a noninferiority margin of 1.5 (Comparator QIV/ Seqirus QIV, equivalent to a difference on the log scale of 0.405465108) will be employed. It is assumed that there is no difference between Seqirus QIV and Comparator QIV (ie, a ratio of 1, difference on the log scale of 0) and that the standard deviation of log (titer) is 1.4.

Under these assumptions and with n evaluable = 1500 in the Seqirus QIV group and 500 in the Comparator QIV the power for 4 GMT ratio endpoints is 99.95% and the power for 4 SCR endpoints is 89.70%. The overall global power of the 8 endpoints is then  $89.7\% \times 99.95\% = 89.66\%$ .

This provides a total N evaluable = 2000 (with 10% dropouts N=2222).

Sample size calculations were performed using SAS v9.3 and PASS v12.0.02.

[Table 3.9-1](#) summarises the list of all primary endpoints with strains, the planned noninferiority margin and underlying assumptions used for the sample size computations.

**Table 3.9-1 Summary of Assumptions Used for Sample Size Calculations**

	H1N1	H3N2	B strains
Test significance level, alpha (1-sided)	2.50%	2.50%	2.50%
Noninferiority Margin for the SCR comparison (%)	10	10	10
Assumed true SCR	50%	50%	50%
Power for SCR comparison tests for each strain (%)	97.32%	97.32%	97.32%
Global Power for 4 SCR Endpoints	89.70%		
Noninferiority Margin for the GMT ratio	1.5	1.5	1.5
Common Standard Deviation of $\log_e(\text{titre})$	1.4	1.4	1.4
Power for GMT ratio tests for each strain (%)	99.99%	99.99%	99.99%
Global Power for 4 GMT ratio Endpoints	99.95%		
Global Power for 8 Co-primary Endpoints	89.66%		

